- Patient of legal age but subject to legal protection measure or unable to express their consent
- Patient suffering from uncontrolled epilepsy
- Patient with visual or auditory disorders
- Patient suffering from claustrophobia or motion sickness
- Patient with face infection
- Patient with dissociative psychiatric pathologies and autism

After consulting the patients' medical records, and checking that there are no exclusion criteria, the investigators will introduce themselves to the patients and their families, informing them that they are eligible and offering them to take part in the study.

[figure not shown]
Patients will be informed that the study aims to investigate the immersive effect of VR during intravenous cannulation procedure, and they will be provided with a patient information sheet and flyer.

If the patient agrees in principle to take part in the study, and after obtaining informed, signed, written consent, each patient will be given a personalized schedule of the various management appointments and the questionnaires used as part of the protocol.

Interventions:

Patients will benefit from the standard of care for their first visit, then they will have a VR session on their second visit, then another session in VR for their third visit. The VR session starts 5 minutes before the intravenous cannulation procedure, 10 minutes during the procedure and 5 minutes after, for a total of 20 minutes. Before and after the intravenous cannulation procedure, the investigator will complete the Case Report Form for data collection from patients.

All participants will complete questionnaires before and after the procedure at visit 1 (V1), V2 and V3. The interval between visits is 3 weeks, in line with clinical practice at the referral centre.

The two options for managing anxiety and general symptoms are:

1) Standards of care (SOC) :

Thalassemia patients require lifelong monthly blood transfusions to survive. During routine visits, an experienced healthcare provider inserts intravenous cannulation under aseptic technique. Children are escorted by parents to offer support and distraction. This short procedure is accompanied by pain and anxiety for all the involved parties.

2) Virtual reality (VR)

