HEALTHY MIND© VR (Paris, France): a 15-minute VR therapeutic session immersing the patient in an artificial world created from computer-generated images using software connected to the PICO 4E headset. The patient can choose one of several types of environments (beach, mountains, lake and others) using synthetic animated images, breathing exercises and advanced psychological/relaxation principles such as cardiac coherence or hypnotic verbal accompaniment.

Variables will be reported in a standardized way in the CRF in the following order:

- Before intravenous cannulation
 - Patient identification number
 - Patient demographics (gender and age)
 - Inclusion and exclusion criteria
 - Patient's VAS for pain intensity
 - Patient's VAS for anxiety
 - Patient's VAS for fatigue
 - Patient's VAS for cramps and heart rate measurement
- After intravenous cannulation:
 - Characteristics of intravenous cannulation. Specificity.
 - Patient's VAS for pain intensity
 - Patient's VAS for anxiety
 - Patient's VAS for fatigue
 - Patient's VAS for cramps and heart rate measurement
 - Patient's VAS for comfort and acceptability of VR headset use

Data collection

	Pre inclusion V0 (*)	Visite 1		Visite 2		Visite 3	
		Before	Post	Before	Post	Before	Post
Screenning and information	✓						
Consent form signed	✓						
Demographic Data ¹		✓					
Physiological data ²		✓	✓	✓	✓	✓	✓
VAS ³ Anxiety, Pain and Fatigue		✓	✓	✓	✓	✓	✓
HAD scale		✓			✓		✓
Patient/Family Satisfaction			✓		✓		
Professional Satisfaction							✓

Expected Outcomes

Primary outcomes: Evaluated by the Visual Analogue Scale (VAS)

- Evaluate the impact of VR-induced 3D immersion on anxiety during cannulations through visualization of Healthy Mind VR therapeutic sessions (using a PICO 4E VR headset). Comparison of patients' anxiety levels before and after the procedure with and without VR. Assessed by visual analog scale (VAS).
- Evaluate the impact of VR-induced 3D immersion pain during cannulations through visualization of Healthy Mind VR therapeutic sessions (using a PICO 4E VR headset). Comparison of patients' pain levels before and after the procedure with and without VR.

Secondary outcomes: Evaluated by the Visual Analogue Scale (VAS)

- Evaluation of fatigue levels after the procedure for patients with and without VR.

- Examine factors associated with boredom and weariness with and without VR.
- Evaluation of patient satisfaction with and without VR.

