- Assessment of healthcare professionals' satisfaction levels during and after the procedure with and without VR.
- Assessment of family members' satisfaction levels during and after the procedure with and without VR.
- Assessment of other outcomes of interest (exploratory)
 - Evaluation of the heart rate with and without VR (cardiac frequency)

Sample size calculation:

Due to the exploratory nature of the study, the sample size was calculated on the basis of the number of possible orders of relaxation sessions, which was calculated as follows: 3 types of options x 3 x 2 = 18 possible session orders.

At least two different patients had to be enrolled for each type of option (i.e. 36 patients), to ensure a homogeneous distribution of the different possible orders of relaxation within the study population. 100 patients had to be enrolled in the study, to take account of patients lost to follow-up and missing data. Study power was set at 80% to demonstrate a clinically significant difference greater than 2, with an alpha threshold of 0.05.

Statistical analysis of primary objectives:

The difference between two sessions (VR vs SOC) will be followed by a comparison of the proportions of patients who achieved at least a 25% improvement in anxiety, pain, fatigue, and depression, assessed by the VAS and HAD scale in post-cannulation procedure. The value provided to patients in the VR session during intravenous cannulation procedure and patients with SOC, will be compared using Student's t-test, after verification of the homoscedasticity hypothesis by a Levene's test.

If this hypothesis is not verified, the Mann-Whitney test will be performed, for which the number of patients required to maintain 90% power is 35 per group. If the reduction is not 25% but only 20%, with a power of 80%, this difference will be highlighted.

A 2-factor repeated-measures ANOVA model (VR vs. non-VR session and time before vs. time after) will be developed. Another statistical model will be developed, in order to see the time and session effect and to see if there is an interaction between the 2 factors. Finally, the correlation between basal anxiety scores on the different VAS, HAD scales will be estimated using Pearson's or Spearman's coefficients; the same statistical approach will be used to assess correlations between basal anxiety and their levels measured after the cycles by the VAS.

Statistical analysis of secondary objectives:

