The difference between two sessions (VR vs SOC) will be followed by a comparison of the proportions of patients who achieved at least a 25% improvement in satisfaction, assessed by the VAS. Comparison will be carried out using the same method used for primary objectives.

Risk factors associated with dissatisfaction will be explored using uni and multivariate logistic regression models.

Overall ethical considerations

This study is useful both for its scientific contribution and for improving the comfort of thalassemia patients undergoing invasive procedures such as intravenous cannulation. Through this study, we will gain insight into the impact of virtual reality as an adjuvant to care for intravenous cannulations.

Our research will be conducted in accordance with the Declaration of Helsinki and the National Act on Research Involving Human Subjects. We will ensure that no coercion or pressure to participate is exerted on patient-participants. Written informed consent will be obtained from each participant. At any time and without explanation, participants may leave the study without any effect on future care, treatment or working conditions.

With the exception of necessary personal data (socio-demographic information), members of the research team will maintain confidentiality with patient information. Participant data will be anonymised or coded as appropriate and stored securely.

Limitations

A limitation of our study is that randomising the order of intervention sessions was not favourable for our investigation. Because our participants all suffer from chronic disease, the most appropriate way to get a baseline for pain and anxiety perception is before exposure to VR intervention. If done in an alternative manner, i.e. starting with a VR session and then not having VR, it would be more likely for patients to over-report their feelings of pain or anxiety, thus skewing the results. Hence, ordering the sessions in the way that was ultimately decided was, we believe, in favour of reducing bias.

The results of this study will be applicable to all population groups which do not fall under our exclusion criteria (as mentioned in the methods).

Project Timeline

	Feb 2024	Mar 2024	15th April – 15th June	July 2024	Aug 2024	Nov-Dec 2024
IRB Submission						
Site preparation, staff training						
Screening and inclusion						
Data management						
Statistical analysis						
Dissertation writing						

Acknowledgements

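### Factors for dissatisfaction are to be sought by logistic regression although satisfaction is described as a VAS rated after both V1 and V2 by the same patients; modelling the VAS itself would be more powerful and would handle the pairing.

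*Combined protocol and SAP*

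**What the plan says.** The whole plan for associated factors is one sentence under Statistical analysis of secondary objectives: "Risk factors associated with dissatisfaction will be explored using uni and multivariate logistic regression models". The sentence before it compares the proportions of patients with "at least a 25% improvement in satisfaction, assessed by the VAS". Under Expected Outcomes, the secondary outcomes, satisfaction among them, are also said to be measured by VAS.

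In the Data collection table, the row "Patient/Family Satisfaction" is ticked post-procedure at Visit 1 and Visit 2 and not at Visit 3. Under Interventions, the order is the same for everyone: "Patients will benefit from the standard of care for their first visit, then they will have a VR session on their second visit". Each patient therefore gives one rating under each condition.

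The plan gives no cut-off for dissatisfaction, expected rate, list of factors or model terms. It does not say whether V1, V2 or both are modelled, or how two ratings from one patient are handled.

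**The concern.** Logistic regression needs a yes/no outcome, so a graded score has to be cut. Patients just either side of the cut-off are then treated as different, and patients far apart on the same side as alike. The cost is power to find real factors, in a study of about 100 patients. Because the cut-off is not fixed, it could also be chosen after the data are seen.

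The pairing raises a second question. Two ratings from one patient are not independent. If both visits are entered into an ordinary logistic model, its standard errors ignore that. At stake is how reliable the list of reported factors will be.

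**Working it through.** **Inputs from the plan.** Scale: VAS. Ratings: V1 post and V2 post, same patients. Enrolment: "100 patients had to be enrolled in the study, to take account of patients lost to follow-up and missing data".

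**Assumptions, because the documents give no figures.** A roughly normal satisfaction score; 10-50% classed as dissatisfied; a factor correlated 0.3 with satisfaction; all 100 patients analysed; two-sided 5% tests.

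**The plan's own figures.** "3 types of options x 3 x 2 = 18 possible session orders" is correct as arithmetic, and two patients for each gives 18 × 2 = 36. The step from 36 to 100 would imply a loss of 1 − 36/100 = 64%, and no dropout rate is stated. None of these figures sizes the regression, so there is no stated figure for it to reproduce.

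**Step 1: information kept after a split.** For a normal score cut so that a proportion p is dissatisfied, the relative efficiency is φ(z_p)² / [p(1 − p)], where z_p is the normal quantile and φ the normal density.
- p = 10%: 0.1755² / 0.09 = 0.34
- p = 50%: 0.3989² / 0.25 = 0.64

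**Step 2: power.** With the VAS kept whole, the Fisher approximation gives atanh(0.3) × √97 = 0.3095 × 9.849 = 3.05, and Φ(3.05 − 1.96) = 86%. After the split, 3.05 is multiplied by the square root of the efficiency. Simulation (1,500 runs per setting, 100 patients, one rating each) gives slightly lower values.

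| Assumed dissatisfied | Information kept | Power by formula | Power of logistic regression, simulated |
|---|---|---|---|
| 10% | 34% | 43% | 41% |
| 15% | 43% | 51% | 48% |
| 20% | 49% | 57% | 55% |
| 30% | 58% | 64% | 62% |
| 50% (median split) | 64% | 68% | 66% |

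The linear model on the same simulated data has about 86% power. Even the median split costs about 20 points.

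**Step 3: if both visits enter one ordinary logistic model.** Let ρ be the correlation between a patient's two yes/no ratings.
- For a factor constant within patient, the true standard error is √(1 + ρ) times the reported one. At ρ = 0.3 the ratio is 1.14, and the nominal 5% error becomes 2[1 − Φ(1.96/1.14)] = 8.6%.
- For the standard-care/VR term, the true standard error is √(1 − ρ) times the reported one. At ρ = 0.3 the error is 2[1 − Φ(1.96/0.837)] = 1.9%, so the test is too cautious.

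Across ρ = 0.2 to 0.7 the formula gives 7.4% to 13.3% for patient-level factors. Simulations with 100 patients, two visits, 10-50% dissatisfied and latent correlations of 0.3-0.7 gave roughly 6-10%. The simulated values are lower because a latent correlation shrinks when the score is cut: at 10-50% dissatisfied, latent values of 0.5-0.7 became about 0.24-0.49 between the yes/no ratings. In the same settings the error for the standard-care/VR term was 0.5-2.2%. With patient-clustered standard errors, the error for patient-level factors returned to 3.7-6.1%.

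**The case against.** The strongest reply is that the sentence is merely brief. It belongs to an exploratory analysis, and a stated cut-off, a short factor list and clustered standard errors would repair it within logistic regression. That would indeed make the analysis valid. It would not recover the power lost in Step 2, which is lost at every cut-off.

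Several stronger readings are tempting, and the documents do not support them:
- **Univariable screening.** The wording fits unadjusted and adjusted odds ratios reported side by side equally well. No selection rule is stated.
- **Pooling of visits.** Nothing says V1 and V2 will be pooled; a separate model per visit fits the text. Step 3 is conditional. Its patient-level figure also does not carry over directly to factors recorded afresh at each visit, such as pre-procedure pain or heart rate.
- **Most of the information lost, and room for only one or two factors.** Both depend on a rate the plan does not give. At ten events per factor, 100 × p / 10 allows one factor at 10% dissatisfied and two at 20%, but three to five at 30-50%. More than half the information is lost only at about 20% dissatisfied or fewer (or, by symmetry, 80% or more).
- **Logistic regression cannot separate VR from care in general.** It can, with a session term or one model per visit. The plan simply lists no terms.
- **Multiplicity.** Eight independent null tests give 1 − 0.95⁸ = 34% chance of at least one p < 0.05, but that applies to any model and is no argument against this one.
- **Steering who is offered VR.** No section says the factors will be used in that way.

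One doubt about the premise also stands. The CRF list under Interventions has a VAS for headset comfort and acceptability but none for satisfaction, and the visit table puts satisfaction on a row apart from the anxiety, pain and fatigue VAS. Family and professional satisfaction are separate outcomes, so the rater is not certain either.

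**Conclusion.** The point holds as a better choice of method for one exploratory secondary analysis. On the plan's own description, a VAS rated twice by the same patients will be reduced to yes/no at an unstated cut-off. Under rough normality, with a factor correlated 0.3 with satisfaction and 100 patients analysed, power falls from about 86% to about 66% at best, and to 41-55% if 10-20% are dissatisfied. A strongly skewed score would change these figures, and fewer analysed patients would lower power under either method.

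The error in the standard errors arises only if both visits are modelled without allowing for the pairing, and its direction depends on the factor. A reader might infer that the plan commits to pooling, or that the reported p-values will always be too small; neither follows from the text.

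**What to change.** Make the main factor analysis a linear mixed model of the V1 and V2 patient satisfaction VAS, with a patient random intercept, session (standard care or VR), and three or four factors fixed in advance, for example age, gender, and pre-procedure anxiety and pain. Label the session-by-factor interactions exploratory. If the VAS is strongly skewed, use robust standard errors or an ordinal model.

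If a yes/no analysis is kept, call it supportive, state the cut-off and the visit or visits, and use GEE or patient-clustered standard errors when both visits are used. State whose satisfaction is modelled, and align the CRF list with the visit table so that the satisfaction VAS appears in both.

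The cost is SAP wording, plus a CRF clarification if the satisfaction VAS is not already on the form. No extra visits or ratings are needed beyond those the schedule already has. The downside is that results are in VAS points rather than odds ratios, and fewer factors may be examined.

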We propose to conduct an interventional cross-over study with a cohort of around 100 patients, where initial data is collected without VR for measuring baseline, then VR is implemented twice in a 3-week interval between sessions. We will investigate the impact of VR software on patients' pain and anxiety during the intravenous cannulation procedure, compared with a standard care program. Our primary outcomes involve assessing patient pain and anxiety, while secondary outcomes are fatigue, boredom, and overall patient satisfaction.

Pain and anxiety will be measured both subjectively (VAS) and objectively (cardiac frequency) as secondary exploratory measures. We will also look to assess healthcare providers' and family members' satisfaction levels pre and post VR intervention. The aim of this study is to evaluate the benefits of VR programs in reducing patients' pain and anxiety.

Introduction

Background and Rationale:

Hemoglobinopathies, specifically β -thalassemia, are a significant health concern in the UAE, affecting 8.5% of the population [1,2]. These genetic disorders often require frequent blood draws, chelation therapy, and transfusions, causing stress and impacting quality of life for patients [3].

Repeated pain in children with chronic diseases such as thalassemia can cause behavioural changes in their adolescence, such as anxiety, social problems, and decreased attention. This condition can further impact the quality of life of thalassaemic children as adults [4]. Therefore, nurses must provide specific interventions to improve the child's comfort during invasive procedures.

Virtual reality (VR) is a technology that enables patients to be projected, via a computer system, into an immersive 3-dimensional virtual world. This specificity gives VR a highly immersive and distracting capacity. VR effectively diverts the patient's attention away from the source of pain, thereby diminishing his or her conscious perception of it [5,6].

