In recent years, the number of studies investigating the use of Virtual Reality (VR) as a non-pharmacological method of reducing anxiety and pain has grown rapidly. Numerous studies have confirmed this analgesic effect of VR on different modalities such as invasive procedures in chronic diseases such as thalassemia [4,7]. These benefits apply to a multitude of interventions in order to improve the management of pain and/or anxiety, such as wound care [8,9], needle insertion in children [10,11], perioperative management [12,13] and chronic pain relief [14].

Therefore, we propose to conduct an interventional cross-over study to investigate the impact of VR software on patients' pain and anxiety during the intravenous cannulation procedure, compared with a standard care program. The aim of this study is to evaluate the benefits of VR programs in reducing patients' pain and anxiety.

Study Aim:

The primary aim of this study is to assess whether VR has a greater therapeutic impact on patient anxiety and pain perception compared to the standard of care during intravenous cannulation

procedures among thalassemia patients. This study will allow us to conclude on the effectiveness of virtual reality as an adjuvant medical device during the intravenous cannulation procedure.

Study Objectives:

- Evaluate the impact of VR-induced 3D immersion on pain and anxiety during cannulations through visualization of Healthy Mind VR therapeutic sessions.
- Comparison of patients' anxiety levels before and after the procedure with and without VR.
- Comparison of patients' pain levels before and after the procedure with and without VR.

Research Hypothesis:

There will be an improvement in the pain and anxiety measurement parameters with the use of virtual reality during the intravenous catheterisation procedure in thalassemia patients.

Methods:

This is an interventional cross-over, single-center study comparing virtual reality and standard care during intravenous cannulation for thalassemia patients at the Thalassemia Center in Dubai. The study is planned between April 2024 and June 2024.

Participants:

Inclusion criteria:

- Patient with diagnosis of thalassemia
- Thalassemia patient undergoing cannulation intravenous procedure
- Patients aged above >7 years (male, female, adults, paediatric, national and non-national) admitted at the referral center of thalassemia in Dubai

Exclusion criteria:

- Pregnant or nursing woman

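### Every patient has standard care at V1 and VR at V2 and V3, so VR cannot be separated from a first-versus-later visit effect, and the bias-reduction and effectiveness statements go further than the design allows

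*Combined protocol and SAP*

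**What the plan says.** The opening summary and the Interventions section fix one sequence for everyone: "initial data is collected without VR for measuring baseline, then VR is implemented twice in a 3-week interval between sessions", and "Patients will benefit from the standard of care for their first visit, then they will have a VR session on their second visit", with VR again at the third. Visits are three weeks apart. Methods gives the design as follows: "This is an interventional cross-over, single-center study comparing virtual reality and standard care during intravenous cannulation for thalassemia patients".

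The primary outcomes are worded as a contrast of before and after readings, for example "Comparison of patients' anxiety levels before and after the procedure with and without VR". The analysis section for the primary objectives plans a t-test or Mann-Whitney comparison of VR with SOC, a comparison of the proportions with at least 25% improvement, and a repeated-measures ANOVA with session (VR or not) and time (before or after) as factors. A further model is to look at their interaction. No model has a visit term.

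The Limitations section acknowledges that the order is not randomised. Its reason is that patients who had VR first might over-report pain or anxiety afterwards without it, and it ends with the belief that "ordering the sessions in the way that was ultimately decided was, we believe, in favour of reducing bias". The Study Aim states: "This study will allow us to conclude on the effectiveness of virtual reality as an adjuvant medical device during the intravenous cannulation procedure".

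The sample-size section calls the study exploratory. It derives its minimum of 36 patients from 18 possible session orders, with two patients for each, so that the orders are evenly spread.

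**The concern.** With one sequence for all patients, the VR indicator and the later-than-first-visit indicator are the same variable. Whatever makes pain or anxiety scores differ between the first study visit and the next two (study novelty, for example) is counted as a VR effect. The trial could then report that VR works when part or all of the difference belongs to the visit.

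Two sentences lead the reader past this. The Limitations section presents the fixed order as an advantage, and the Study Aim promises a conclusion on effectiveness without qualification. The sample-size text adds to the confusion because it describes several session orders spread evenly over the patients, which is not the design being run.

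**Working it through.** **1. Post-procedure values.** Let d_v be the visit effect at visit v and β the VR effect. The expected means are μ + d_1 at V1, μ + d_2 + β at V2 and μ + d_3 + β at V3. The mean of the VR visits minus the SOC visit is

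β + (d_2 + d_3)/2 − d_1.

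The visit part does not shrink with sample size. As a rank check, intercept + V2 + V3 + VR has 4 columns and rank 3, so VR is not estimable. If drift is assumed strictly linear and the VR effect constant, intercept + linear visit + VR has 3 columns and rank 3. VR can then be estimated, but three visit means leave 0 degrees of freedom to test that assumption.

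**2. Before-after change.** Let a_v be a shift common to both readings of a visit, and g_v a visit effect on the change. The before mean is μ + a_v. The after mean is μ + a_v + c + g_v, plus β at VR visits. The contrast of changes is

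β + (g_2 + g_3)/2 − g_1.

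The a_v cancel and the g_v do not. As a rank check, visit levels + time + VR × time has 5 columns and rank 5, so VR × time is estimable if drift is only a common shift. Adding visit × time gives 7 columns and rank 6, so it is not estimable if the change itself may differ by visit.

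**3. Timing of the before reading.** VR starts 5 minutes before cannulation, and the case report form is completed before cannulation. The protocol does not say whether the before VAS comes before the headset goes on. If VR has already altered that reading by b, the contrast of changes estimates β − b plus the g terms. The cancellation then also removes part of the VR effect.

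**4. Possible size.** The documents give no drift, SD or correlation, so these inputs are assumptions: no VR effect, two-sided 0.05, a paired test, a 0-10 scale, and SD of within-patient differences 2.5, 3.0 or 3.54 (2.5 × √2). The rejection rate comes from the noncentral t distribution with n − 1 degrees of freedom and noncentrality drift/(SD/√n). For example, 0.5/(2.5/√100) = 2.0 gives 51%, and 0.5/(2.5/√36) = 1.2 gives 22%. The two values of n are the plan's enrolment (100) and its minimum before losses (36).

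| Drift in the analysed outcome | n | SD 2.5 | SD 3.0 | SD 3.54 |
|---|---|---|---|---|
| 0.5 | 100 | 51% | 38% | 29% |
| 0.5 | 36 | 22% | 16% | 13% |
| 1.0 | 100 | 98% | 91% | 80% |
| 1.0 | 36 | 65% | 49% | 38% |

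The type of drift matters. In simulation with 100 pairs, a 1-point shift common to both readings was declared significant 98% of the time on post values (SD 2.5) but 5% of the time in the interaction. A 1-point drift in the change gave 98% on post values and 80% in the interaction (SD 3.54). The t-test with Levene's check in the plan reads as an unpaired test. With 100 per session, SD of differences 2.5 to 3.5 and correlation 0.3 to 0.7, it rejects less often: 2% to 36% for 0.5 point and 24% to 95% for 1 point.

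**5. Session orders.** The plan's arithmetic reproduces: 3 × 3 × 2 = 18, and 18 × 2 = 36. But one SOC and two VR sessions can be ordered in only 3!/(1! × 2!) = 3 ways, and the plan uses 1. If the 18 refers to VR environments, the intervention description says "The patient can choose one of several types of environments", so their distribution is not controlled either.

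**The case against.** The order is not hidden. It is listed as a limitation, the bias sentence is hedged as a belief, and it is comparative: it sets this order against VR first and does not claim freedom from bias. The sample-size section calls the study exploratory. All of this stands and lowers the severity. It does not repair the Study Aim, which has no such qualifier. Avoiding one possible order effect also does not show that bias is reduced on balance.

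A reader might infer that the result is probably biased by habituation. The documents do not support that. They say "Thalassemia patients require lifelong monthly blood transfusions to survive", so V1 is generally not a first cannulation, and nothing shows that drift is likely. A reader might also infer that every analysis is confounded by any order effect. That is too strong, because a common level shift cancels in the interaction, subject to the timing question. Nor is expectation of benefit from a visible headset a consequence of the order: it would affect an unblinded VR-versus-SOC comparison in any sequence.

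The rejection rates are hypothetical and depend on how many pairs are complete, which is why both 100 and 36 are shown. A 1-point drift would rarely produce an observed difference of 2 (0.003% at SD 2.5 and 0.2% at SD 3.54, with 100 pairs), if the plan's target difference of more than 2 is read as VAS points. The plan does not make 2 a decision rule, however, and with 100 pairs a difference of 0.50 to 0.70 is already significant.

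It is fair to say that patients do move from SOC to VR, so the cross-over label is partly a matter of terms, and that the count of 18 orders is a separate inconsistency, not evidence of confounding.

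**Conclusion.** The point holds as an error in what the text claims, and it should be corrected. It does not show that the findings will be wrong. The aliasing of VR with later visits follows from the visit schedule alone and needs no assumed figures. It applies to post-procedure values and to any visit effect on the before-after change. Only untestable assumptions, such as strictly linear drift with a constant VR effect, would separate the two.

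The size of any bias is unknown. The range for a 0.5-point drift (13% to 51% false-positive findings over the two sample sizes, paired test) rests wholly on assumed drift, scale and SD. The design supports a statement about the observed difference between V1 without VR and V2/V3 with VR. It does not support attributing that difference to VR alone, nor a net reduction of bias. The 18-order basis for the sample size contradicts the single sequence, or is left uncontrolled if it means environments.

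**What to change.** 1. **Study Aim:** limit the conclusion to the observed difference between V1 without VR and V2/V3 with VR, not attributed to VR alone.
2. **Limitations:** replace the bias sentence with: *All patients had SOC at V1 and VR at V2 and V3. The effect of VR cannot be separated from a first-versus-later visit effect on post-procedure values or on the before-after change. If the before reading precedes the start of VR, a level shift common to both readings of a visit is removed when the change is analysed.* Also state whether the before VAS is taken before the headset is put on.
3. **Opening summary and Methods:** describe the design as a single-group, fixed-sequence study.
4. **Sample size:** reconcile the 18 orders and their even distribution with the one sequence used, and do not present them as the basis of the sample size.
5. **Analysis:** report V3 minus V2, and pre-cannulation VAS across V1 to V3, as supportive descriptions. State that they may flag drift but cannot remove the confounding. V3 minus V2 mixes drift with repeated VR exposure. Pre-cannulation VAS may reflect anticipation of VR or, if taken after VR starts, VR itself.

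The cost is wording in four places, one clarification of timing and two descriptive summaries of data already scheduled. Visits and procedures do not change. The downside for the sponsor is a less favourable claim.
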